### 5.2.4 Safety laboratory parameters

For the assessment of laboratory parameters, blood and urine samples will be collected by the trial site at the times indicated in the [Flow Chart](#) after the subjects have fasted for at least 10 h except at Day 1, 6 h. For retests, at the discretion of the investigator or designee, overnight fasting is not required. The parameters that will be determined are listed in Tables 5.2.4: 1 and [5.2.4: 2](#). Reference ranges will be provided in the ISF.

Manual differential WBC (white blood cell) count or urine sediment examinations will only be performed if there is an abnormality in the automatic blood cell count or in the urinalysis, respectively.

The trial will use a standard and a reduced safety lab. Respective timing is given in Flow Chart.

Standard safety lab is given in Table 5.2.4:1.

Reduced safety lab panels only include:

- AST, ALT, creatinine kinase (CK), CK Isoenzyme myocardial band (MB) [only if CK is elevated], Myoglobin, Lactic Dehydrogenase: planned at Day 1 predose and 6h only

The following safety lab parameters will be determined only at specified study visit:

- Thyroid Stimulating Hormone (TSH), Total cholesterol, Triglyceride: planned at screening visit only
- Fibrinogen, ALP (Alkaline Phosphatase), GGT (Gamma-Glutamyl Transferase), Lipase, Albumin, Uric Acid: planned at screening visit and EoT visit only

Table 5.2.4: 1 Routine laboratory tests

| Functional lab group  | BI test name [comment/abbreviation]  |
|---|--|
| Haematology   | Haematocrit
Haemoglobin
Red Blood Cell (RBC) Count/Erythrocytes
Reticulocytes, absolute and relative
WBC/Leucocytes
Platelet Count/Thrombocytes (quant) |
| Automatic WBC differential, relative                                | Neutrophils/Leukocytes; Eosinophils/Leukocytes; Basophils/Leukocytes; Monocytes/Leukocytes; Lymphocytes/Leukocytes   |
| Manual differential WBC (if automatic differential WBC is abnormal) | Neutrophils/Leukocytes; Eosinophils/Leukocytes; Basophils/Leukocytes; Monocytes/Leukocytes; Lymphocytes/Leukocytes   |
| Coagulation   | Activated Partial Thromboplastin Time
Prothrombin time – INR (International Normalization Ratio)
Fibrinogen **   |

\*: At screening visit only

\*\*: At screening and EoT visit only

\*\*\*: Reduced safety lab, Day 1 predoze & 6h only

Proprietary confidential information © 2021 Boehringer Ingelheim International GmbH or one or more of its affiliated companies

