#### **7.3.4 Safety analyses**

Safety will be assessed as defined by the endpoints listed in Section [2.1.2](#) and [2.2.2](#) based on the TS. Safety analyses will be descriptive in nature and will be based on BI standards.

For all analyses the treatment actually administered (= treatment at onset) to the subject will be used (any deviations from the randomised treatment will be discussed in the minutes of the Report Planning Meeting).

Treatments will be compared in a descriptive way. The placebo group in the safety evaluation will consist of all subjects treated with placebo, regardless of the dose group in which they were treated. The test treatment groups will be compared to the placebo group in a descriptive way. Tabulations of frequencies/proportions will be used for the evaluation of categorical (qualitative) data, and tabulations of descriptive statistics will be used to analyze continuous (quantitative) data.

Measurements (such as ECGs, vital signs, or laboratory parameters) or AEs will be assigned to treatments (see Section [4.1](#)) based on the actual treatment at the planned time of the

Proprietary confidential information © 2021 Boehringer Ingelheim International GmbH or one or more of its affiliated companies

measurement or on the recorded time of AE onset (concept of treatment-emergent AEs). Therefore, measurements planned or AEs recorded prior to intake of the trial medication will be assigned to the screening period, those between the trial medication intake and end of REP (see Section [1.2.7](#)) will be assigned to the treatment period. Events occurring after the REP but prior to trial termination date will be assigned to 'follow-up'. These assignments including the corresponding time intervals will be defined in detail in the TSAP. Note that AEs occurring after the last per protocol contact but entered before database lock will be reported to Pharmacovigilance only and will not be captured in the trial database.

Additionally, further treatment intervals (called analysing treatments) may be defined in the TSAP in order to provide summary statistics for other than the above periods, such as combined treatments, on-treatment totals, or periods without treatment effects (such as screening and post-study intervals).

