6.7 BASELINE, TIME WINDOWS AND CALCULATED VISITS

The baseline value is defined as the last measurement before administration of trial medication (BI 474121 or Placebo).

Section 6.1 of the CTP: *Exact times of measurements outside the permitted time windows will be documented. The acceptable time windows for screening and the end of trial examination are provided in the CTP Flow Chart.*

Study measurements and assessments scheduled to occur ‘before’ trial medication administration on Day 1 are to be performed and completed within a 3 h-period prior to the trial drug administration (including blank values for PK and biomarkers).

The acceptable deviation from the scheduled time for vital signs, ECG, start of first RR measurement in orthostatic tests, and laboratory tests will be ± 15 min for the first 4 h after trial drug administration, ± 30 min thereafter on Day 1, ± 60 min on Day 2, and ± 120 min from 48 h post administration onwards.

Starting from 48 h post administration, a deviation from the scheduled time for PK and biomarker sampling as well as for AE questioning of ± 120 min is acceptable.

Adherence to time windows will be checked via the consistency check listings at the RPM.

Unscheduled measurements of laboratory data, orthostatic testing and vital signs data will be assumed to be repeat measurements of the most recent scheduled measurement (e.g. for follow-up or confirmation of a particular value). Therefore, unscheduled measurements will be assigned to the planned time point of the previous scheduled measurement.

There will be a centralised evaluation of the 12-lead ECG recordings at the time points and for the ECG recordings specified in [Table 6.7: 1](#):

Table 6.7: 1 Time schedule of 12-lead ECG recordings

Visit	Day	Planned time [hh:mm] (relative to drug administration)	Study phase	Central evaluation
1	-28 to -1		Screening	NA
2	1	-01:00	Baseline	First ECG of each of the 3 triplicate baselines
		-00:45		
		-00:30		
		00:30		
		01:00		
		01:30		
		02:00		
		03:00		
		04:00		
		06:00		
		08:00		
		12:00		
	2	24:00		
		34:00		
	3	48:00		
	4	72:00		Single ECG
	5	96:00		Single ECG
3	8 to 15		End of trial examination	NA

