The analyses of laboratory data will be descriptive in nature and will be based on BI standards [BI-KMED-BDS-HTG-0042] (12). Analyses will be based on normalised values, which means transforming to a standard unit and a standard reference range. The original values will be analysed if the transformation into standard unit is not possible for a parameter.

Laboratory data will be analysed qualitatively via comparison of laboratory data to their reference ranges. Values outside the reference range as well as values defined as possibly clinically significant will be flagged in the data listings.

Clinically relevant findings in laboratory data will be reported as baseline conditions (at screening) or as AEs (during the trial) if judged clinically relevant by the investigator, and will be analysed as such.

It is the investigator's responsibility to decide whether a lab value is clinically significantly abnormal or not (at the RPM at the latest).

Descriptive statistics of laboratory data including change from baseline will be calculated by planned time point based on the worst value of the subject at that planned time point (or assigned to that planned time point).

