7.8.3 Vital signs

Descriptive statistics over time including change from baseline will be performed for vital signs (blood pressure and pulse rate). In the listing the change from baseline will also be displayed. For vital signs, descriptive statistics will be calculated by planned time point based on the last value of the subject at that planned time point (or assigned to that planned time point), and will be displayed by treatment and in total.

Descriptive statistics over time including change from baseline (by treatment and in total) will also be provided for the orthostatic test results to enable checking of orthostatic hypotension occurrence. Subjects should have spent at least 5 minutes in the supine position before blood pressure and pulse rate will be measured the first time. Further 2 measurements will be performed immediately after standing up and after 3 minutes in a standing position. An orthostatic hypotension is defined as a decline in systolic blood pressure of ≥ 20 mmHg or a decline in diastolic blood pressure of ≥ 10 mmHg within the first three minutes after standing up. Orthostatic hypotension is assessed for all post dose time points.

Body temperature will be listed only.

Clinically relevant findings will be reported as baseline conditions (at screening) or as AEs (during the trial) if judged clinically relevant by the investigator, and will be analysed as such.

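### SAP 6.7 lets an unscheduled laboratory, orthostatic or vital-signs result taken shortly after dosing be summarised in a pre-dose row

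*SAP*

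**What the plan says.** SAP 6.7 sets one rule for three classes of data: "Unscheduled measurements of laboratory data, orthostatic testing and vital signs data will be assumed to be repeat measurements of the most recent scheduled measurement". It concludes that "unscheduled measurements will be assigned to the planned time point of the previous scheduled measurement". Nothing is said about the case where trial medication is taken between the two measurements.

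The summaries build on that assignment. For laboratory data (SAP 7.8.2), the by-time-point statistics are "based on the worst value of the subject at that planned time point (or assigned to that planned time point". For vital signs (SAP 7.8.3) they are "based on the last value of the subject at that planned time point (or assigned to that planned time point". The same section tabulates orthostatic results over time, and it checks for orthostatic hypotension at post-dose time points only.

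Baseline has its own definition in SAP 6.7: "The baseline value is defined as the last measurement before administration of trial medication (BI 474121 or Placebo".

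**The concern.** Treating an unscheduled value as a repeat is reasonable when both measurements lie on the same side of the dose. It is not reasonable across the dose, because a value taken after drug intake does not re-measure the pre-dose state. The rule as written makes no such distinction.

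Unscheduled safety measurements are usually taken because something looks wrong. Protocol 5.2.6.1.4 foresees one: ALT, AST and total bilirubin in an unscheduled blood test when hepatic injury is suspected. Orthostatic testing is included to assess haemodynamic effects (Protocol 1.4.3), after vasodilation was seen in animals (Protocol 5.4). At stake is whether the laboratory, orthostatic and vital-signs summaries place such a result on the correct side of dosing. In groups of six active subjects, a single misplaced value is visible in a row of descriptive statistics.

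**Working it through.** No sample-size or error-rate figure is involved, so there is nothing of that kind to reproduce. The check applies the SAP 6.7 rule literally to the schedule.

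**Inputs.** Scheduled times come from the Flow Chart and Protocol 5.2.4. The reduced panel (AST, ALT, CK, CK-MB if CK is raised, myoglobin, LDH) is taken at Day 1 pre-dose and 6 h. The standard panel is next taken at 24 h. For six further analytes the protocol states: "Fibrinogen, ALP (Alkaline Phosphatase), GGT (Gamma-Glutamyl Transferase), Lipase, Albumin, Uric Acid: planned at screening visit and EoT visit only". Orthostatic tests are at Day 1 pre-dose, then 2, 4 and 8 h. Blood pressure and pulse rate are at Day 1 pre-dose, then 0.5 h onwards.

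**Rule.** Assigned slot = latest scheduled time at or before the unscheduled measurement. The exposed window therefore runs from dosing (0 h) to the first scheduled post-dose time.

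| Measurement | Last slot before dosing | First slot after dosing | Post-dose window filed before dosing |
|---|---|---|---|
| Laboratory, rule read by sampling time | Day 1 pre-dose | 6 h | 0–6 h |
| Orthostatic test | Day 1 pre-dose | 2 h | 0–2 h |
| Blood pressure, pulse rate | Day 1 pre-dose | 0.5 h | 0–0.5 h |

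Reduced-panel analytes have the 0–6 h window on either reading of the rule. The SAP does not say whether the previous scheduled measurement is meant per sampling time or per analyte. If it is meant per analyte, two laboratory windows become longer:

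| Analytes (per-analyte reading only) | Last slot before dosing | First slot after dosing | Window |
|---|---|---|---|
| Standard panel outside the reduced panel, e.g. total bilirubin, creatinine, potassium | Day -3 to -1 visit, or screening if that sample was omitted | 24 h | 0–24 h |
| The six screening/EoT-only analytes | Screening | EoT, Day 8–15 | 7 to 14 days (8 − 1 = 7; 15 − 1 = 14) |

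**What the tables then show.**

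- *Laboratory.* Assume AST is 30 U/L pre-dose and 95 U/L in an unscheduled sample at 3 h. Both values sit in the Day 1 pre-dose slot, and the worst is max(30, 95) = 95 U/L. If the other five subjects of an active group are also assumed to be at 30 U/L, the pre-dose mean is (5 × 30 + 95)/6 = 40.8 U/L instead of 30 U/L. Baseline stays at 30 U/L, so the pre-dose row would carry a change from baseline of 95 − 30 = 65 U/L for that subject. These values are illustrative only.
- *Vital signs.* The last-value rule picks the later measurement, so any unscheduled value in the first 30 minutes replaces the true pre-dose value, whether or not it is abnormal.
- *Orthostatic tests.* A drop found in an unscheduled test within 2 h of dosing is filed as pre-dose. On a literal reading it is then not part of an assessment restricted to post-dose time points. The SAP states no separate rule for choosing among repeat orthostatic tests.

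**Weight of one subject.** 1/6 = 16.7% of an active group; 1/8 = 12.5% of pooled placebo (4 groups × 2 = 8).

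**The case against.** The strongest reply is that little depends on these rows. Baseline excludes post-dose values by definition, so changes from baseline at later time points are unaffected. All individual values are listed, and out-of-range and possibly clinically significant laboratory values are flagged (SAP 7, 7.8.2). Findings the investigator judges clinically relevant become adverse events, which are placed by recorded onset time (Protocol 7.3.4, SAP 6.1). Hepatic injury is an AESI with its own table (SAP 7.8.1). Dose escalation rests on the safety review in Protocol 3.1, not on these tables. All of this stands and sets the size of the point. It does not correct the summary row, and the adverse-event route depends on the investigator's judgement.

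Some stronger readings are tempting, and the documents do not support them:

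- *That laboratory exposure certainly lasts 24 h, or until EoT.* SAP 6.7 speaks of classes of data, not analytes. Read by sampling time, the window is 0–6 h for every analyte. ALP or GGT drawn because of a raised scheduled 6 h ALT would then be filed at 6 h or later, which is correctly post-dose.
- *That the value formally leaves the treatment period.* Protocol 7.3.4 says "measurements planned or AEs recorded prior to intake of the trial medication will be assigned to the screening period", but an unscheduled test has no planned time of its own. The same section leaves detailed assignment to the TSAP, and SAP 6.1 defines its phases for adverse events.
- *That baseline is contaminated or the signal is lost.* The baseline definition and the listings rule this out.

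Finally, the analysis data set plan and reviewer's guide (SAP 6.1), the laboratory standard (SAP 7.8.2) and redacted parts of the SAP cannot be seen and might contain an exception. The visible SAP text has none.

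**Conclusion.** The point holds as a defect in a stated rule. Applied as written, SAP 6.7 puts an unscheduled post-dose result in a pre-dose row if it is taken within 6 h (laboratory), 2 h (orthostatic) or 0.5 h (vital signs) of dosing. The consequence is a wrong entry in descriptive by-time-point tables and, for orthostatic drops, a possible omission from the post-dose hypotension assessment. The longer laboratory windows are conditional on a per-analyte reading that the SAP neither states nor excludes.

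The conclusion assumes that the rule is programmed literally and that no unseen document overrides it. It matters only if such a measurement occurs, and the documents give no basis for estimating how often. The primary endpoint does not depend on it.

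**What to change.** Add to SAP 6.7 that an unscheduled laboratory, orthostatic or vital-signs measurement taken after administration of trial medication is never assigned to a time point before administration. Where no earlier scheduled post-dose measurement exists, show the value as an on-treatment unscheduled value by actual time, with change from baseline. Include any such orthostatic test in the post-dose orthostatic hypotension assessment in SAP 7.8.3. State in the same place whether the previous scheduled measurement is identified per sampling time or per analyte.

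The cost is one programming condition on recorded times and an occasional extra table row with few subjects, often one. No new data are needed. Protocol 7.3.4 already leaves detailed assignment of measurements to the TSAP, so this is the natural place for the rule.

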## 6. INVESTIGATIONAL PLAN

### 6.1 VISIT SCHEDULE

Exact times of measurements outside the permitted time windows will be documented. The acceptable time windows for screening and the end of trial examination are provided in the [Flow Chart](#).

Study measurements and assessments scheduled to occur 'before' trial medication administration on Day 1 are to be performed and completed within a 3 h-period prior to the trial drug administration (including blank values for PK and biomarkers).

The acceptable deviation from the scheduled time for vital signs, ECG, start of first RR measurement in orthostatic tests, and laboratory tests will be  $\pm$  15 min for the first 4 h after trial drug administration,  $\pm$  30 min thereafter on Day 1,  $\pm$  60 min on Day 2, and  $\pm$  120 min from 48 h post administration onwards.

Starting from 48 h post administration, a deviation from the scheduled time for PK and biomarker sampling as well as for AE questioning of  $\pm$  120 min is acceptable.

If several activities are scheduled at the same time point in the Flow Chart, ECG should be the first and meal the last activity. Furthermore, if several measurements including venipuncture are scheduled for the same time, venipuncture should be the last of the measurements due to its inconvenience to the subject and possible influence on physiological parameters (except orthostatic testing).

For planned individual plasma concentration sampling times and urine collection intervals, refer to the Flow Chart. While these nominal times should be adhered to as closely as possible, the actual sampling times will be recorded and used for the determination of pharmacokinetic parameters.

If a subject misses an appointment, it will be rescheduled, if possible. The relevance of measurements outside the permitted time windows will be assessed no later than at the Report Planning Meeting.

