At Visits 1 and 3 (screening and end of trial examination), single ECGs will be recorded and will not be transferred to the central ECG lab. Three triplicate ECGs will be recorded as the baseline before drug administration, but only the first ECG of each of the 3 baseline triplicates will be transferred to the database. At all other time points (except for ECGs on day 4 and 5 of Visit 2), 1 triplicate ECG will be recorded, but only the first single ECG of the triplicate will be transferred to the database. The baseline value of an ECG variable is defined as the mean of the ECG variable values prior to drug administration.

For the exposure response analyses, pairs of ECG variables and corresponding plasma concentrations will be built using the same planned time points, e.g., the HR change from baseline and the plasma concentration measured at planned time 0:30 will build one pair. Whether a time deviation between PK blood sampling time and corresponding ECG recording is too big and the pair has to be excluded from the analysis will be decided no later than at the RPM. Data exclusion due to time deviations will only be applied to subjects on active study treatment.

In line with the tolerated time deviations of previous trials in this project, the acceptable maximum time deviations between ECG recordings and plasma concentration sampling are proposed to be

- 10 minutes for up to 1 hours (including) after dosing,
- 20 minutes for time points from more than 1 hour to 12 hours after dosing, and
- 60 minutes for time points at 12 hours or later after dosing,

Pairs with time deviations exceeding those specified above will be excluded from exposure-response analyses. When the sampling time of the blood sample or the ECG recording is not available, the pair will also be excluded.

As the clinical trial protocol permits larger time deviations of ECG measurements from the planned time in the flow chart, and consequently indirectly accepts larger time deviations of ECG and PK sampling, a sensitivity analysis will be done. For the sensitivity analysis, the acceptable maximum time deviation between ECG recording and plasma concentration sampling are proposed to be

- 15 minutes for up to 4 hours (including) after dosing,
- 30 minutes for time points from more than 4h to 24h after dosing,
- 60 minutes for time points at 24h to 48h after dosing,
- 120 minutes for time points at 48 hours or later after dosing.

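### The sensitivity windows for pairing ECGs with plasma samples are tighter than the main windows at 1.5, 2, 3 and 4 h, and the main window at 12 h is ambiguous

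*SAP*

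**What the plan says.** SAP Section 6.7 pairs each ECG value with the plasma concentration at the same planned time and drops pairs whose two measurements lie too far apart. In the main analysis the largest allowed gap is 10 minutes up to and including 1 h. The second main limit is worded "20 minutes for time points from more than 1 hour to 12 hours after dosing, and"; the third main limit is worded "60 minutes for time points at 12 hours or later after dosing". The SAP attributes these limits to earlier trials in the project.

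It then notes that the protocol lets ECGs deviate further from planned time and "consequently indirectly accepts larger time deviations of ECG and PK sampling, a sensitivity analysis will be done". The first sensitivity limit is "15 minutes for up to 4 hours (including) after dosing". The second sensitivity limit is "30 minutes for time points from more than 4h to 24h after dosing", the third sensitivity limit is "60 minutes for time points at 24h to 48h after dosing", and the last one is 120 minutes from 48 h.

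The limits bite in the active arms only: "Data exclusion due to time deviations will only be applied to subjects on active study treatment".

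The pairs feed the random coefficient model in SAP Section 7.8.4, which is described as exploratory and is run for QTcF and again for HR.

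**The concern.** The stated reason for the sensitivity analysis is that larger gaps may be acceptable, so its data set should contain every main-analysis pair plus some extra ones. Between 1.5 and 4 h the limit moves the other way, from 20 to 15 minutes. A pair 18 minutes apart at 2 h stays in the main analysis and drops out of the sensitivity analysis.

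With pairs entering at some times and leaving at others, a changed slope or a changed estimate at geometric mean Cmax cannot be put down to wider windows. An unchanged result is not clean reassurance either, since gains and losses could offset. The analysis still has some value as a mixed test because it does admit extra pairs at other times.

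The 12 h overlap is a separate defect. Two programmers could apply 20 or 60 minutes and both follow the text. The choice also decides whether the sensitivity analysis loosens or tightens the limit at that time.

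**Working it through.** **Inputs.** The post-dose ECG times are in SAP Table 6.7: 1, and the protocol Flow Chart has a plasma sample at all 14. Both sets of limits are in SAP Section 6.7. Active subjects: 6 per dose group × 4 groups = 24 (Protocol Section 3.1). ECG tolerances against planned time are in Protocol Section 6.1.

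**Step 1: limits side by side (minutes).**

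| Planned time | Main | Sensitivity | Sensitivity relative to main |
|---|---|---|---|
| 0.5, 1 h | 10 | 15 | wider |
| 1.5, 2, 3, 4 h | 20 | 15 | **narrower** |
| 6, 8 h | 20 | 30 | wider |
| 12 h | 20 or 60 | 30 | wider or narrower |
| 24 h | 60 | 30 or 60 | equal if 60 |
| 34 h | 60 | 60 | equal |
| 48 h | 60 | 60 or 120 | wider if 120 |
| 72, 96 h | 60 | 120 | wider |

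The sensitivity bins also overlap at 24 h and 48 h. Protocol Section 6.1 allows 60 minutes on Day 2 and 120 minutes from 48 h, so I read these as 60 and 120 and do not count either as narrower.

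**Step 2: count.** Planned active pairs: 14 × 24 = 336.

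- Narrower at 4 times: 4 × 24 = 96 pairs, and 96/336 = 28.6%.
- Wider at 7 times (0.5, 1, 6, 8, 48, 72, 96 h): 7 × 24 = 168 pairs.
- Equal at 2 times (24, 34 h).
- Open at 1 time (12 h). If its main limit is 60, the sensitivity limit is narrower at 5 of 14 times.

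**Step 3: can an 18-minute gap arise within the protocol?** At 2 h, an ECG 15 minutes early is within its tolerance. If the sample is 3 minutes late, the gap is 15 + 3 = 18 minutes. No numerical window is broken, because the protocol gives one for plasma sampling only late on: "Starting from 48 h post administration, a deviation from the scheduled time for PK and biomarker sampling" is accepted up to 120 minutes. Since 15 < 18 ≤ 20, the main analysis keeps the pair and the sensitivity analysis excludes it.

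**Step 4: how many pairs might move?** The documents give no gap distribution, so this step is assumption only. Let the gap G be normal with mean μ and SD σ, the same at all times. The share kept in the main set but dropped from the sensitivity set at 1.5 to 4 h is

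P(15 < |G| ≤ 20) = [Φ((20−μ)/σ) − Φ((15−μ)/σ)] + [Φ((−15−μ)/σ) − Φ((−20−μ)/σ)].

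The expected number added is 48 × P(10 < |G| ≤ 15) for 0.5 and 1 h, plus 72 × P(20 < |G| ≤ 30) for 6, 8 and 12 h, plus 72 × P(60 < |G| ≤ 120) for 48, 72 and 96 h. The last term is practically zero here. If the 12 h main limit is 60, the middle multiplier becomes 48.

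| μ, σ (min) | P(15 < \|G\| ≤ 20) | Dropped, of 96 | Added, 12 h main = 20 | Added, 12 h main = 60 |
|---|---|---|---|---|
| 0, 5 | 0.26% | 0.2 | 2.1 | 2.1 |
| 0, 8 | 4.8% | 4.6 | 8.1 | 7.8 |
| 0, 10 | 8.8% | 8.5 | 11.9 | 10.9 |
| 5, 5 | 2.1% | 2.1 | 6.7 | 6.7 |
| 5, 8 | 8.1% | 7.7 | 11.1 | 10.3 |
| 5, 10 | 10.8% | 10.4 | 14.1 | 12.5 |

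Worked row (μ = 0, σ = 8): 2 × [Φ(2.5) − Φ(1.875)] = 4.8%, and 96 × 0.0484 = 4.6 pairs dropped. Added: 48 × 0.1505 + 72 × 0.0122 = 7.2 + 0.9 = 8.1.

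The non-zero mean is included because Protocol Section 5.2 places the ECG before the blood sample. The value of 5 minutes is my assumption.

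**The case against.** The best defence is that 15/30/60/120 minutes is not arbitrary: it reproduces the ECG tolerances in Protocol Section 6.1. On that view the plan runs the model under two sensible window sets, which need not be nested, and agreement between them still says something about robustness. This explains where the numbers came from but does not justify them. A tolerance for one measurement against planned time is not a limit on the gap between two measurements, and the SAP's own rationale is that larger gaps are accepted.

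Second, the tighter limit may seldom bite. If the ECG is within its 15 minutes and the sample is drawn exactly on time, the gap cannot exceed 15 minutes. The protocol also asks that sampling keep close to nominal times. This stands. The 96 pairs are those scheduled at the affected times, not those that would be lost; even the largest assumed loss is 10.4/336 = 3.1% of planned active pairs.

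Third, the wording may settle 12 h. The SAP marks inclusive upper bounds explicitly at 1 h and 4 h but not at 12 h, and the next bin opens at 12 h. That favours 60 minutes but does not say so, and it would make 12 h a fifth narrower time. SAP Section 10.1.4, cited for model details, is not in the available text and might clarify this.

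Finally, pair exclusions are settled by the Report Planning Meeting, and the model is exploratory. Both are true and limit the consequences. Neither removes the contradiction in the written rule.

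**Conclusion.** The concern holds. The inversion at 1.5, 2, 3 and 4 h follows directly from the text, with no assumption and under any reading of the bin edges. The 12 h overlap is also real in the text available. As written, the sensitivity data set need not contain the main data set, so the analysis does not do what its rationale says.

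The numerical effect is unknown. The illustrative figures rest on assumed normal gaps with one distribution at all times. Apart from the tightest case (mean 0, SD 5), they put losses and gains at a broadly similar order, which is why the comparison would be mixed. The reading of 24 h and 48 h as 60 and 120 minutes rests on Protocol Section 6.1. Only the exploratory QTcF and HR exposure-response analyses are touched. It should be corrected, but it does not threaten the trial's main conclusions.

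**What to change.** At each time, set the sensitivity limit to the larger of the main limit and the present sensitivity limit, and write every bin so that edges belong to one bin only.

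- Sensitivity: up to and including 1 h, 15 minutes; after 1 h to 4 h inclusive, 20; after 4 h and before 24 h, 30; from 24 h and before 48 h, 60; from 48 h, 120.
- Main: assign 12 h explicitly to the 20-minute or the 60-minute bin, from the source the sponsor used for the main limits. If it is 60, give 12 h a 60-minute sensitivity limit as well, so that the 30-minute bin ends before 12 h.
- Report the number of pairs added and dropped at each time point; with these bins none should be dropped.

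From 1.5 to 4 h the two limits would then be equal, so nothing is relaxed there. That is consistent with the rationale and keeps the sets nested; testing a wider gap at those times would need a limit above 20 minutes, which the documents do not supply.

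The cost is a few lines of SAP text and one program parameter table.
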